Subjects may be withdrawn from the clinical investigation at any time due to voluntary withdrawal, investigator decision, or other unforeseen circumstances. Regardless of cause, all early terminations must be documented clearly in the Case Report Form (CRF) (attached to this protocol), including the specific reason for withdrawal. The following outlines the criteria and procedures for subject withdrawal:

Early Termination – General Considerations: All early exits from the study will be promptly recorded, and the rationale for withdrawal should be documented in the CRF to ensure traceability, transparency, and compliance with study oversight requirements.

Failure During Initial Use - While inclusion/exclusion criteria with pre-screening and in-office assessment that is part of the standard operating procedure will optimize appropriate participant selection, they may not be 100% predictive of device compatibility. In some instances, a subject may meet pre-screening criteria but be unable to use the Obi Gen 3 device safely or effectively during initial use. These cases will be identified early—typically on the first day of the trial—and such individuals will be withdrawn from the study. These withdrawals must be clearly documented in the CRF and the reason and relevant observational notes.

Voluntary Withdrawal of Consent - Subjects (or their legal representatives) have the right to withdraw consent and discontinue participation in the study at any time and for any reason, without penalty or loss of benefits. If informed consent is withdrawn, no additional data will be collected from the subject beyond the point of withdrawal. All data previously collected up to the point of withdrawal may be retained and used for analysis unless the subject explicitly requests full data removal, as outlined in the consent form.

Investigator-Initiated Withdrawal - If, at any time during the investigation, the Principal Investigator determines that continued participation poses an unforeseen risk to the subject's well-being or safety—or for other clinical, behavioral, or protocol-related reasons—the subject may be withdrawn from the study. The justification for investigator-initiated withdrawal must be documented in the CRF, and the subject (or caregiver) must be informed of the decision following ethical and regulatory standards.

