Given the minimal-risk nature of the study, no intensive or intrusive tracking methods (e.g., home visits) will be used. Participants will be informed during the consent process that follow-up is optional and that they may discontinue participation at any time without consequence.

iii.) whether and how subjects are to be replaced.

Given the nature of this usability study and the relatively small, targeted sample size, subjects who withdraw voluntarily or are lost to follow-up during the study period will not be replaced. However, if a subject withdraws before completing any meaningful portion of the data collection (e.g., before starting the Obi Gen 3 trial period or before completing in-office assessments), the study team may recruit an additional participant to maintain representation across stakeholder groups (providers, caregivers, and patients). Replacement will occur only as needed to ensure data completeness or demographic diversity aligned with the study's exploratory objectives.

d) Point of enrollment.

Participants are considered enrolled in the study after providing informed consent (or assent, where applicable) and after completing an initial in-office clinical assessment by a qualified provider (typically an occupational therapist) as outlined in SOP220. This point marks the subject's formal inclusion in the study and the beginning of data collection activities using the HIPAA-compliant Qualtrics platform.

e) Point of randomization, if applicable. Randomization does not apply to this investigation.

f) Total expected duration of the clinical investigation.

The total expected duration of this clinical investigation is approximately three (3) months, spanning from April 2025 through June 2025. This time frame includes:

- Pre-screening, recruitment, and enrollment of participants across all stakeholder groups (providers, caregivers, and patients),
- Completion of a one-week home/community trial of the Obi Gen 3 device by up to 60 participants,
- Post-trial survey and interview data collection,
- Final data analysis and reporting of usability outcomes.

The duration also accommodates staggered enrollment and rolling recruitment, which will occur on a first-come, first-served basis until target sample sizes are reached. The study timeline may be adjusted slightly based on participant availability and operational needs but is not expected to exceed the nine-month window.

g) Expected duration of each subject's participation.

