Given the short duration and minimal risk nature of this usability study, the expected drop-out rate is anticipated to be low (less than 10%). Participants will be engaged for a one-week home or community-based trial of the Obi Gen 3 device,. The limited time commitment, non-invasive nature of participation, and flexibility of remote data collection (via Qualtrics and telephone interviews) are expected to support high retention.

Potential reasons for early withdrawal or loss to follow-up may include:

- Lack of interest or time to complete the trial period or follow-up activities
- Health-related issues or changes in caregiving responsibilities
- Technological issues or accessibility barriers (e.g., inability to access electronic surveys)
- In rare cases, discomfort or dissatisfaction with the device

Because the study does not involve treatment, diagnostic procedures, or invasive interventions, death is not anticipated and is not an endpoint. Any withdrawal or loss to follow-up will be documented with reason, when available. Data collected prior to withdrawal will be included in the analysis, consistent with an as-treated approach.

f) The rationale for the number of procedures to be performed by a single user as part of the learning curve and how these data are to be analysed, if applicable.

Given that this investigation evaluates the usability of a robotic feeding device designed for individuals with upper extremity impairments, caregivers, and providers, it is important to account for the initial learning period associated with device setup, operation, and integration into daily routines. The one-week trial period with a minimum expectation of five completed meals per patient/caregiver dyad is designed to reflect a realistic and sufficient exposure to allow users to become familiar with the device and overcome early learning curve effects.

This threshold was selected based on preliminary feedback from internal evaluations and stakeholder consultations, which indicated that users typically require **3–5 sessions**, to feel comfortable with basic functions (e.g., powering on, positioning the spoon, switching food compartments). For providers, the requirement to recommend and assess at least one patient supports evaluation of the device within their existing workflow, allowing observation of setup, training, and follow-up in a practical setting.

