Although this study does not include formal repeated-measures testing or time-stamped use logs, reported experience over multiple uses (i.e., across several meals and settings) will provide insight into how effectively users can learn to operate the device independently. This data will inform training recommendations and design refinements to support intuitive, low-burden use in real-world environments.

g) Pass/fail criteria to be applied to the results of the clinical investigation.

As a design validation study, the primary objective of this clinical investigation is to determine whether the Obi Gen 3 production equivalent device meets its formally documented user needs and intended use across three key stakeholder groups: patients, caregivers, and providers. The pass/fail criteria are based on usability outcomes aligned with ISO 13485 and FDA design validation requirements. The following criteria must be met for the device to be considered as having “passed” the clinical investigation:

Primary Endpoints: Acceptance criteria is based on safety and quality risk (see IFD-DES-054-1, Design Validation Plan, and IFD-DES-054-2, Design Validation Protocol). Note: Design Validation planning involves more than just human subject testing. This CIP covers only the human subject portion.

Intended Use: For all subjects that complete the 1-week trial, the following must be met:

- ICF performance qualifier for Functional Eating must drop at least one severity level (ex. “severe” to “moderate”) for 85% of patients.
- No Serious Adverse Device Effects (SADE), Serious Health Threat, or Unanticipated Serious Adverse Device Effect (USADE).

User Needs: For all subjects that complete the 1-week trial, 50% of respondents must be in favor that the requirement has been fulfilled (see IFD-DES-051-1 Validation Plan)

If the investigation meets or exceeds these thresholds across all stakeholder groups, the design will be deemed to have passed and is considered validated. If one or more criteria are not met, the results will be analyzed to determine if design modifications, additional training resources, or workflow adjustments are necessary prior to commercialization.

h) The provision for an interim analysis, criteria for the termination of the clinical investigation on statistical grounds, where applicable.

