Given the usability-focused, non-interventional design of this clinical investigation, the approach to managing missing, unused, or spurious data will prioritize transparency, traceability, and context-based interpretation rather than imputation or statistical correction.

Missing Data - All efforts will be made to minimize missing data by:

- Using structured and user-friendly electronic data collection tools (Qualtrics),
- Providing reminders for survey completion, and

- Offering support to participants during the trial period.

When data are missing, the specific nature and reason for the missing information (e.g., participant withdrawal, technical issues, non-response) will be recorded in the study database. Missing data will not be imputed, as the primary goal is descriptive analysis rather than inferential statistical modeling. Analyses will be conducted using available data only, and the extent of missingness will be reported for each data element.

Unused or Incomplete Data - Incomplete survey responses or interviews that do not meet minimal content thresholds (e.g., <50% of questions answered) may be excluded from individual item-level analysis but will be retained in the dataset for auditability. The rationale for excluding such data will be documented in the data analysis plan and in the final study report.

Spurious or Implausible Data - Any values that are clearly spurious (e.g., internal inconsistencies, out-of-range responses) will be flagged during data quality checks. If these data cannot be resolved through source verification (e.g., interview notes, metadata review), they will be excluded from analysis and annotated accordingly in the dataset with justification.

Participant Drop-outs - Participants who withdraw from the study after enrollment will be asked, if willing, to provide a brief reason for withdrawal. Drop-outs will be tracked, and their status will be clearly documented in the final dataset. Data collected prior to withdrawal will be included in the analysis unless the participant requests removal of their data per the informed consent agreement. The rate and pattern of drop-outs or early discontinuation will be described in the final study report to assess potential biases or operational challenges affecting the usability evaluation.

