n) Exploratory analysis and sensitivity analysis (e.g. to explore robustness of results of primary and secondary analysis with respect to different methods used for handling missing data), if applicable.

Not applicable. This study is concerned with qualitative insights and limited scope of variables.

o) Procedures for reporting any deviation(s) from the original statistical analysis plan.

Any deviation from the original statistical analysis plan (SAP), whether related to the analysis population, analytical methods, handling of missing data, or presentation of results, will be documented in the protocol deviation log and addressed in the final clinical investigation report.

If deviations are necessary during the course of data analysis—such as the inclusion of alternative summary measures, subgroup analyses not originally specified, or adjustments to account for unforeseen data collection challenges—these will be:

- Clearly documented with a justification for the change,

- Dated and signed by the responsible investigator or data analyst,
- Reviewed by the principal investigator and, if applicable, the sponsor, and
- Reported transparently in the final report, along with the impact of the deviation on the interpretation of the study outcomes.

All such deviations will be made prior to unblinding or final data lock to ensure analytical integrity and avoid bias in interpretation. Because this is an exploratory usability study using descriptive and qualitative methods, formal pre-specification of statistical hypotheses is limited; however, the principles of transparency, traceability, and justification will be upheld for any post hoc analytical decisions.

p) For multicentre clinical investigations, a strategy for handling the potential imbalance of the numbers of subjects across investigation sites.

Not applicable. This study involves a single site.

q) A strategy for pooling data, if applicable.

Not applicable based on the study design.

A.8. Data Management

a) Methods (e.g. CRF) for data entry and collection.

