Complaints regarding the device, including notice of an adverse event, or adverse device effect will be processed in accordance with DESIN LLC's SOP120, Return and Service Procedures, which include processes and timing for adverse event handling, documentation and reporting to regulatory authorities.

DESIN LLCs Service Manager will be provided a copy of the study device serial numbers in order to flag complaints resulting from the study. Any complaints, including notification of adverse events, resulting from study devices will be promptly sent to [name] & PI [name].

For the purposes of this study, all AEs/SAEs/SADEs/USADE, or Serious Health Threats (events) must be collected from enrollment (ICF signature) through study completion. The principal investigator is ultimately responsible for reporting such events to the IRB.

Events should be recorded in standard medical terminology rather than the subject's own words.

- Note the duration by entering the date of onset and date of resolution.
- Note the worse intensity of the event as mild/moderate or severe.
- Note the frequency of the event as a single episode, intermittent, or continuous.
- Note the actions taken as none, medication, procedure, or other.
- Note the relationship to study procedure or device as not-related, unlikely, possibly related, probably-related, or causal relationship.

g) Details of the process for reporting device deficiencies.

Device deficiencies, including handling of adverse events, and adverse device effects (including timeframes for reporting), will be processed in accordance with the company's complaint handling procedure, SOP120, including D-FRM-005, Complaint Form. Device deficiencies will be recorded using the Complaint form and reviewed by the quality and engineering teams for tracking and analysis.

Corrective/Preventive Action will occur in accordance with SOP080, CAPA procedures, and any advisory notices or recalls will be executed per SOP070, Non-Conformance procedures.

h) List of foreseeable adverse events and anticipated adverse device effects, together with their likely incidence, mitigation, or treatment.

There are no anticipated serious adverse events (SAEs) based on the device's classification and prior real-world use. The following are foreseeable but rare adverse device effects during use of the Obi Gen 3:

- Frustration or anxiety related to unfamiliar technology or difficulty in control coordination

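### The pass/fail criteria count only patients who complete the 1-week trial, so enrolled patients withdrawn because they cannot use the device never count against it

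*Protocol*

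**What the plan says.** A.7 g) gives the only rule by which the design is declared validated. Its first part begins "Intended Use: For all subjects that complete the 1-week trial, the following must be met". Two criteria follow: a drop of at least one severity level on the ICF performance qualifier for functional eating in 85% of patients, and "No Serious Adverse Device Effects (SADE), Serious Health Threat, or Unanticipated Serious Adverse Device Effect (USADE"). The User Needs criterion (50% in favour) carries the same restriction to completers.

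A.6.3 c), under failure during initial use, accepts that screening may not be fully predictive. Patients who cannot use the device safely or effectively are "identified early—typically on the first day of the trial—and such individuals will be withdrawn from the study", with the reason recorded in the CRF. Under A.6.3 d) a subject is enrolled after consent "and after completing an initial in-office clinical assessment by a qualified provider", and under A.6.4 a) only those who pass that assessment take the device home. Only subjects who finish the trial have the follow-up office assessment.

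Other passages bear on such patients without changing the rule:

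- A.7 a) takes everyone who consented and completed the survey, on an as-treated basis and without imputation.
- A.7 e) 6) states that "the expected drop-out rate is anticipated to be low (less than 10"%).
- A.7 m) says "The rate and pattern of drop-outs or early discontinuation will be described in the final study report to assess potential biases".
- A.7 n), on sensitivity analysis, reads "Not applicable. This study is concerned with qualitative insights and limited scope of variables".
- A.14 f) says adverse events and serious device effects "must be collected from enrollment (ICF signature) through study completion".
- A.6.1 f) lets recruitment continue after losses that occur before the minimum trial period is completed. A.6.3 c) iii) allows it only where no meaningful part of data collection has been done.

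**The concern.** The primary question is whether the design fulfils its intended use in the patients it is given to. A patient whom the protocol's own screening judged suitable, who took the device home and could not use it, is a direct negative answer. A.7 g) treats that patient as a non-participant. The exclusion depends on the outcome, so its bias has one direction: it favours passing.

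The safety criterion has the same fault. Read literally, a serious device effect that led to withdrawal would not fail the device, although a serious event is a likely reason for not completing.

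The two replacement passages add to the problem. They differ on when a further patient may be recruited, and neither says that the original subject stays in the denominator. Device failures could therefore be replaced by new recruits and still be absent from the decision.

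**Working it through.** **Inputs from the protocol.** 20 patients (A.6.3 h); threshold 85% (A.7 g); expected all-cause drop-out below 10% (A.7 e 6). The protocol derives neither the 85% nor the sample size from a formula, so there is no calculation of its own to reproduce.

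**Assumptions, not in the protocol.** *f* is the probability that an enrolled patient cannot use the device and is withdrawn. *s* is the probability of improvement among the rest. There are no other losses and no replacement.

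**Step 1: the bar.** The minimum number of responders among *n* patients is ceil(0.85 × *n*).

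| Withdrawn | Completers | 0.85 × n | Needed | Needed as % of 20 enrolled |
|---|---|---|---|---|
| 0 | 20 | 17.00 | 17 | 85% |
| 1 | 19 | 16.15 | 17 | 85% |
| 2 | 18 | 15.30 | 16 | 80% |
| 3 | 17 | 14.45 | 15 | 75% |
| 4 | 16 | 13.60 | 14 | 70% |

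With all 20 counted, 17 responders are always needed. Seventeen responders also satisfy the completer rule for any number withdrawn, so every pass on all patients is a pass on completers. The converse fails from two withdrawals on.

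**Step 2: probability of passing (exact binomial).**

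- Completer rule: sum over *w* of Bin(*w*; 20, *f*) × P(X ≥ ceil(0.85(20 − *w*)) | 20 − *w*, *s*).
- All counted: P(X ≥ 17 | 20, (1 − *f*)*s*).

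With *s* = 0.95:

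| f | P(2 or more withdrawn) | Completers | All 20 counted |
|---|---|---|---|
| 1% | 0.02 | 0.975 | 0.972 |
| 2% | 0.06 | 0.968 | 0.955 |
| 3% | 0.12 | 0.962 | 0.933 |
| 5% | 0.26 | 0.955 | 0.876 |
| 10% | 0.61 | 0.948 | 0.672 |
| 20% | 0.93 | 0.948 | 0.257 |

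The 10% and 20% rows lie outside the protocol's expectation of less than 10% for all causes together. They show how the rule behaves if that expectation is wrong.

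**Step 3: given a number of withdrawals, *s* = 0.95.** One: 0.933 under both rules. Two: 0.942 in completers (16 of 18) against 0.774 with all counted (17 of 18 must improve). Three: 0.950 against 0.418.

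**Step 4: a device below the bar.** Fix true success among all enrolled at 80%, so *s* = 0.80/(1 − *f*).

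- *f* = 5%, *s* = 0.842: 0.49 in completers against 0.41 with all counted.
- *f* = 10%, *s* = 0.889: 0.70 against 0.41.

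At the same overall success, the completer rule passes more often when more of the failures are outright inability to use the device.

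**Step 5: the other passages.** The inclusion of pre-withdrawal data (A.7 e 6 and m), the drop-out description (A.7 m) and the event collection window (A.14 f) govern description and collection. None returns a non-completer to the denominator of A.7 g). A patient withdrawn on day 1 has no post-trial qualifier that could be included.

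**The case against.** The strongest reply is that the effect is small where the protocol expects to be. Drop-out below 10% of 20 patients means at most one, and one withdrawal does not move the bar. At device-failure rates of 1% to 3% the gap in the chance of passing is 0.003 to 0.029. That stands as far as it goes. But the drop-out figure is an expectation and not a limit, and even at a true rate of 5% two or more withdrawals occur with probability 0.26.

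Second, the study is descriptive, withdrawals are recorded and reported, and missing a criterion leads to further analysis and not to rejection. It is true that nothing is hidden. A.7 g) is still a binary rule, and meeting it means that the design is considered validated.

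Third, some day-1 failures may be eligibility misses, and scoring them as not improved assigns an unmeasured value. The first half is fair. It argues for showing the CRF reasons, because these patients had all passed the protocol's own screening. On the second half, counting a documented inability to use the device as a failure defines the outcome from a recorded fact and does not impute a score.

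Fourth, the safety reading is literal, and nothing suggests the sponsor would ignore a serious device effect. That is probably so, but the acceptance rule should say it.

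Finally, the validation plan and validation protocol cited for acceptance criteria are not available here and may define the population differently. If they do, A.7 g) needs reconciling with them.

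**Conclusion.** The concern holds. As written, A.7 g) leaves out of the primary decision those enrolled patients for whom the device failed outright, and the resulting error can only favour passing. With 20 patients and no replacement, the effect on the 85% criterion is nil for one withdrawal and begins at two, where 16 of 18 completers passes although only 80% of those enrolled improved. The effect on the chance of passing depends on assumed rates. With 95% success among the rest it is negligible at 1% device failures, 0.955 against 0.876 at 5%, and 0.948 against 0.672 at 10%. The fault in the safety criterion does not depend on these assumptions; it follows from the wording. Because the defect lies in the primary decision rule and is cheap to correct, it should be corrected before the rule is applied.

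**What to change.** - **A.7 g), 85% criterion.** Compute it in all enrolled patients who received Obi3 for the home/community trial. Count withdrawal for inability to use the device as not improved, and state that this is an outcome definition based on the CRF reason, consistent with the no-imputation rule in A.7 a) and m). Keep the completer result as a secondary display.
- **A.7 n).** Replace the current entry with a sensitivity analysis showing losses for unrelated reasons both as missing and as failures.
- **A.7 g), safety criterion.** Apply it to all exposed subjects, so that it matches the collection period in A.14 f).
- **A.7 g), User Needs.** Keep observed respondents, include any survey answers from withdrawn subjects, and report the number of device-related withdrawals by CRF reason beside each result. Impute no answers.
- **A.6.1 f) and A.6.3 c) iii).** Reconcile them, and state that an added recruit never removes the original subject from the denominator.
- **A.7 a) and A.7 m).** Align the population and drop-out wording with these changes.

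The cost is wording in six places. No new data are needed, since withdrawal reasons already go into the CRF and events are already collected from consent. The reported success figure may be less favourable.

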Subject Death - In the rare and unforeseen event of a participant's death during the study period, the site investigator or their designated representative must notify the IRB and DESIN LLC within 24 hours of becoming aware of the event. Death will be recorded as a reason for early study termination in the subject's CRF. While Obi Gen 3 is a Class I device with minimal risk, this reporting protocol ensures compliance with good clinical practice and transparency.

ii.) documentation of efforts to be made to trace subjects that are lost to follow-up and possible reasons

This study involves minimal risk and a short duration of participation for most subjects (approximately one week), with optional follow-up within one month for those whose survey responses warrant an optional semi-structured interview conducted by telephone. Despite this, the research team recognizes the importance of accounting for all enrolled subjects and will make reasonable efforts to trace those lost to follow-up. If a participant fails to complete the post-trial survey within one week following the designated trial period, the following steps will be taken:

- **Reminder Emails/Text Messages:** The HIPAA-compliant Qualtrics platform will send an initial automated reminder email and/or text message.
- **Follow-Up Contact:** If no response is received within 3–5 business days, study personnel will make up to two additional attempts to reach the participant by email, text, or phone. (if contact information is available).
- **Documentation:** All follow-up attempts will be documented, including date, time, method of contact, and any responses received.
- **Optional Withdrawal Confirmation:** If a participant expresses that they no longer wish to continue, this will be documented, and their status will be updated as voluntarily withdrawn.
- **Data Retention:** Any partial data collected before loss to follow-up will be retained and analyzed per IRB approval and applicable data use procedures.

Possible Reasons for Loss to Follow-Up May Include:

- Changes in caregiver or patient availability

- Loss of interest or perceived burden of participation
- Technology-related challenges (e.g., issues with email, survey links)
- Medical changes or competing life demands
- Unreachable contact information (e.g., email address no longer active)

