Devices used in during the study will be returned to DESIN LLC, visually inspected, functionally evaluated, cleaned, disinfected and otherwise reconditioned as needed in accordance with DESIN LLC's SOP120. These devices will then be approved to enter the company's trial device fleet. These devices will be used with new prospective customers.

A.6.5 Monitoring Plan

General outline of the monitoring plan to be followed, including access to source data and the extent of source data verification planned.

There is no official monitoring plan developed. However, to ensure adequate monitoring of the study, the principal investigator and/or study team shall cooperate with DESIN LLC. This includes, but is not limited to, allowing the assessment of facilities utilized for this study, providing access to subject report forms, and subject medical records reasonably requested.

A.7. Statistical Design and Analysis

With reference to A.5 and A.6, the description of and justification for statistical design and analysis of the clinical investigation shall cover the following.

a) Analysis population (e.g. intention-to-treat, per-protocol, as-treated) and procedures that take into account all the data.

This clinical investigation is a non-randomized, non-comparative, mixed-methods usability study intended to evaluate whether the production equivalent Obi Gen 3 robotic feeding device meets the documented user needs and intended use across stakeholder groups. As such, the primary focus of the statistical design is on descriptive and qualitative analysis rather than hypothesis testing or inferential statistics.

All participants who complete informed consent and the survey be included in the analysis population. Given the non-interventional nature of the study, the analysis will follow an as-treated approach, with all available data from each stakeholder group included in the final analysis. Participants who after consent but before completing any trial procedures will be excluded from the analysis population. Missing data will be documented but not imputed, as the primary intent is to assess observed usability and feedback trends.

b) Descriptive statistics of baseline data, treatments, safety data and where applicable, primary and secondary endpoints.

Descriptive statistics will be used to summarize:

- Baseline demographic and clinical characteristics, including age, gender, diagnosis, and prior experience with assistive technology.

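### The zero-event safety pass criterion counts only subjects who complete the week, so a serious device effect that ends use does not count against the device

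*Protocol*

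**What the plan says.** Section A.7 g) (pass/fail criteria) opens the intended-use criteria with "Intended Use: For all subjects that complete the 1-week trial, the following must be met". Two bullets follow. The first asks for a drop of at least one severity level on the functional-eating qualifier in 85% of patients. The second is the safety criterion: "No Serious Adverse Device Effects (SADE), Serious Health Threat, or Unanticipated Serious Adverse Device Effect (USADE". If the thresholds are met across stakeholder groups, "the design will be deemed to have passed and is considered validated".

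Other sections bear on who is a completer and on what happens to safety data:

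- **A.6.3 c) i), withdrawal.** A subject found to "be unable to use the Obi Gen 3 device safely or effectively during initial use" is withdrawn, typically on the first day. The investigator may withdraw a subject when "continued participation poses an unforeseen risk". "Death will be recorded as a reason for early study termination".
- **A.7 a), analysis population.** "All participants who complete informed consent and the survey be included in the analysis population". The same paragraph also says that all available data are used on an as-treated basis.
- **A.7 e) 6), drop-out.** "Data collected prior to withdrawal will be included in the analysis, consistent with an as-treated approach". A.7 m) says the same, unless the participant asks for removal.
- **A.14 c), definitions.** A Serious Health Threat is a situation that endangers a participant or other people.
- **A.14 f), reporting.** Events are collected from consent signature to the end of the study.

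**The concern.** Completing the week is not independent of the outcome that the bullet is meant to detect. A serious device effect is a likely reason for a subject to stop, and stopping takes the subject out of the set to which the criterion applies. The criterion can then be met, and the design declared validated, while a device-caused serious event that ended use is on record. A zero-event rule is written to prevent exactly that, and it is the only safety pass criterion stated in this protocol.

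The restriction also fits poorly with the rest of the document. A Serious Health Threat is a situation that may affect people who are not subjects, so it cannot sensibly be counted per completer. The collection window in A.14 f) is wider than the set on which A.7 g) gives its verdict. Nor does A.7 g) define completion: a subject who stops after the five-meal minimum in the synopsis but before the week ends could be read either way.

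**Working it through.** The protocol gives no event rate, error rate or power for this criterion, so there is no figure of its own to reproduce. The check has three steps.

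**1. Does any section widen the rule?** A.7 e) 6) and A.7 m) keep data from before withdrawal in the analysis, but A.7 g) names its own population for the pass decision and they do not alter it. A.7 a) is unclear on this point: one sentence conditions the analysis population on the survey, and another admits all available data. Neither mentions the pass rule. The synopsis (primary safety endpoint), A.10 c), A.14 e), A.14 f) and A.14 j) cover recording, reporting and ad hoc review. None of them changes the verdict in A.7 g).

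**2. One event.** Input: 20 patients (A.6.3 h). Suppose one has a serious device effect that ends use and the other 19 complete.

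- As worded: 0 of 19 completers have an event, so the criterion is met.
- All exposed subjects counted: 1 of 20, so the criterion fails.

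More generally, let q be the share of serious device effects that end use. Given exactly one event, the chance of meeting the criterion is 0 with all exposed subjects and q with completers only.

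**3. Prior chance.** The only record in the protocol is more than 3,000 devices sold with no adverse event (A.1.1, A.4 b). Taken at face value, the one-sided 95% upper bound is 1 − 0.05^(1/3000) = 0.0998%, about 0.1% per device. For n = 20 and an assumed per-patient risk p, with patients without an event counted as completers:

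- all exposed: (1 − p)^20
- completers only: (1 − p(1 − q))^20

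| Assumed p | All exposed | Completers, q = 0.25 | q = 0.5 | q = 0.8 | q = 1 |
|---|---|---|---|---|---|
| 0.1% | 0.980 | 0.985 | 0.990 | 0.996 | 1.000 |
| 0.5% | 0.905 | 0.928 | 0.951 | 0.980 | 1.000 |
| 1% | 0.818 | 0.860 | 0.905 | 0.961 | 1.000 |

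Example at p = 0.1%, q = 0.5: 0.999^20 = 0.980 against 0.9995^20 = 0.990. The last column shows the structural fault: if every serious device effect ends use, the completer version is met with certainty whatever the risk. The 0.5% and 1% rows lie five and ten times above the bound. They are shown only because the record counts devices sold, not patients using Obi3. The protocol gives neither p nor q.

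**The case against.** The strongest case on the other side is that nothing would be hidden. A serious event in a non-completer would be collected and reported to the sponsor and the IRB, could prompt an ad hoc review (A.14 j), and would feed the updated risk management report (A.4 b). Failing A.7 g) only leads to an analysis of whether changes are needed before commercialization. A.7 g) also points to validation documents that are not shown, and says that this plan covers only the human-subject part of validation. The lead-in was probably written for the 85% bullet. Failure on initial use is mainly about compatibility and is not in itself a serious device effect, and a death matters here only if it is device-related. Finally, on the protocol's own record the difference is about one percentage point.

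Most of this is fair and limits the consequence. Surveillance is not at fault, a drafting slip is plausible, the withdrawal rules show routes to non-completion and not serious events as such, and the probabilities rest on assumed inputs. What does not stand is the inference that the rule can be left alone. None of these sections governs the verdict in A.7 g), and a pass rule should not depend on readers ignoring its own lead-in. The unseen documents may state the criterion for all exposed subjects, but then the protocol conflicts with them and still needs correction.

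**Conclusion.** The concern holds. As worded, the only safety pass criterion in the protocol leaves out subjects who do not complete the week, and so leaves out a serious device effect that ends use. One such event among 20 patients turns a failure on this criterion (1 of 20) into a pass (0 of 19, if the others complete).

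The unconditional effect is small if the device record carries over to Obi3: 98.0% against 99.0% at an assumed 0.1% risk with half of events ending use. It would be 90.5% against 95.1% at 0.5%, and 81.8% against 90.5% at 1%. The risk and the use-ending share are assumptions throughout. The conclusion does not rest on them; it rests on the wording of A.7 g) and on the absence of any visible section that extends it. This should be fixed before the criterion is applied.

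**What to change.** Take the safety bullet out of the completer clause in A.7 g) and state it on its own, for example: *No SADE or USADE in any enrolled subject exposed to Obi3, and no Serious Health Threat as defined in A.14 c) arising in the investigation, whether or not the 1-week trial or the survey is completed.* Add to A.7 a) that the survey condition does not limit this criterion. Keep the completer clause only for the criteria meant to describe completers, and check that the cited validation plan and validation protocol use the same population.

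The cost is one or two sentences in A.7 g) and A.7 a). No new data are needed, because A.14 f) already has events collected from consent signature to the end of the study. The change concerns only who is counted in the pass rule and leaves the withdrawal rules as they are.
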